##### 8.1.1.1 Psoriasis Area and Severity Index (PASI)

PASI100 is defined to be equal to 1 if the percentage improvement from Baseline in the PASI scores is 100% and 0 if the percentage improvement from Baseline is less than 100%. This definition is introduced for the purpose of identifying subjects who respond to the treatment (1 = responder, 0 = non-responder).

PASI scoring of psoriatic plaques is based on three criteria: redness (R), thickness (T), and scaliness (S). Severity is rated for each index (R, S, T) on a 0-4 scale (0 for no involvement up to 4 for very marked involvement). The body is divided into four areas comprising the head (h), upper extremities (u), trunk (t), and lower extremities (l). In each of these areas, the fraction of total surface area affected is graded on a 0-6 scale (0 for no involvement; up to 6 for 90% - 100% involvement).

The various body regions are weighted to reflect their respective proportion of BSA. The composite PASI score is then calculated by multiplying the sum of the individual-severity scores for each area by the weighted area-of-involvement score for that respective area, and then summing the four resulting quantities as follows (note for R, T, and S scores are as follows: 0 = none, 1 = slight, 2 = moderate, 3 = marked, and 4 = very marked):

$$\text{PASI} = (0.1 \times (R_h + T_h + S_h) \times A_h) + (0.2 \times (R_u + T_u + S_u) \times A_u) \\ + (0.3 \times (R_t + T_t + S_t) \times A_t) + (0.4 \times (R_l + T_l + S_l) \times A_l)$$

where

$R_h, R_u, R_t, R_l$  = redness score of plaques on the head, upper extremities, trunk, and lower extremities, scored 0-4 respectively;

$T_h, T_u, T_t, T_l$  = thickness score of plaques on the head, upper extremities, trunk, and lower extremities, scored 0-4 respectively;

$S_h, S_u, S_t, S_l$  = scaliness score of plaques on the head, upper extremities, trunk, and lower extremities, scored 0-4 respectively;

$A_h, A_u, A_t, A_l$  = numerical value translation of % area of psoriatic involvement score for the head, upper extremities, trunk, and lower extremities, respectively (where 0 = 0% [clear], 1 =  $\geq 0\%$  to  $< 10\%$ , 2 = 10% to  $< 30\%$ , 3 = 30% to  $< 50\%$ , 4 = 50% to  $< 70\%$ , 5 = 70% to  $< 90\%$ , and 6 = 90% to 100%).

The highest potential PASI score is 72 for severe disease; the lowest is 0 for no psoriasis lesions. PASI scores are treated as continuous. The percent improvement in PASI scores from Baseline will be computed as:

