$$\text{Percent improvement from Baseline} = 100 \times \frac{\text{Baseline PASI} - \text{Post Baseline PASI}}{\text{Baseline PASI}}$$

If a subject has experienced an improvement, this measure will be positive. If a subject has experienced a worsening in their condition, this measure will be negative.

If a subject is missing 1 or 2 severity measurements for a certain region, the average of the remaining severity measurement(s) within that region will be utilized to substitute for the missing severity measurement(s) in that region. If the area of affected skin and/or all severity measurements for up to 2 regions are missing, then the missing (R+T+S) x A for a region will be substituted by the average of the available (R+T+S) x A. Otherwise, the PASI will be set to missing.

### 8.1.1.2 PASI100 Response at Week 16

The primary efficacy variable, PASI100 at Week 16, is a categorical response variable and is defined to be equal to 1 if the percentage improvement from Baseline to Week 16 in the PASI scores is 100% and 0 if the percentage improvement from Baseline to Week 16 is less than 100%. This definition is introduced for the purpose of identifying subjects who respond to the treatment (1 = responder, 0 = non-responder). The definition of percentage improvement from Baseline is given in Section 8.1.1.1.

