### 8.1.2 Primary analysis of the primary efficacy variable

The analysis of the primary efficacy variable (PASI100 at Week 16) will be based on the RS. A stratified Cochran-Mantel-Haenszel (CMH) test will be performed, where region and prior biologic exposure (yes/no) will be used as stratification variables.

Treatment comparisons between bimekizumab and secukinumab will be made based on the CMH test using the p-value for the general association. For the assessment of non-inferiority, a non-inferiority margin of 10% will be used and evaluated based on the CI for the stratified Mantel-Haenszel risk difference between bimekizumab and secukinumab. The evaluation of superiority will use pairwise treatment comparisons based on the CMH test using the p-value for the general association. The odds ratio and associated confidence interval (CI) based on the Wald test will be presented.

To calculate the stratified Mantel-Haenszel risk difference, the method of Greenland and Robins (1985) is used. For each combination of strata, a 2x2 table of treatment group and response is created. A theoretical 2x2 table for a given stratum is shown below, where n = a+b+c+d.

Treatment Group	Response	
	Yes	No
Bimekizumab	a	c
Secukinumab	b	d

Given that structure, the stratified Mantel-Haenszel risk difference, standard error, and two-sided (1-α)\*100% confidence interval may be written as follows:

$$RD_{MH} = \frac{\sum_i ((a_i * (b_i + d_i) / n_i) - (b_i * (a_i + c_i) / n_i))}{\sum_i ((a_i + c_i) * (b_i + d_i) / n_i)}$$

$$SE_{MH} = \sqrt{\frac{\sum_i \left\{ \frac{[a_i * c_i * (b_i + d_i)^3] + [b_i * d_i * (a_i + c_i)^3]}{(a_i + c_i) * (b_i + d_i) * n_i^2} \right\}}{\left\{ \sum_i \left[ \frac{(a_i + c_i) * (b_i + d_i)}{n_i} \right] \right\}^2}}$$

$$CI_{MH} = RD_{MH} \pm \text{probit}(1 - (\alpha/2)) * SE_{MH}$$

For the assessment of non-inferiority of bimekizumab to secukinumab, the lower 97.5% confidence limit for the stratified Mantel-Haenszel risk difference will be considered. If that value is greater than -10%, then non-inferiority will have been established.

NRI will be used to account for missing data in the primary analysis. Specifically, any subject who withdraws from IMP prior to Week 16 or who has missing data for the primary efficacy variables at the Week 16 time point will be considered a nonresponder.

The number and percentage of subjects who are PASI100 responders at Week 16 will be summarized.

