### 8.3.9 Modified Nail Psoriasis Severity Index (mNAPSI) score

Psoriatic nail disease will be evaluated at the Baseline visit using the mNAPSI. All affected nails will be scored (0 to 3) for onycholysis/oil drop dyschromia, nail plate crumbling, and pitting and will be scored (0 for “no” or 1 for “yes”) for leukonychia, nail bed hyperkeratosis, splinter

haemorrhages and red spots in the lunula. The score for an individual nail ranges from 0 to 13 with higher scores indicative of more severe nail disease. The total mNAPSI score is the sum of the scores for each individual nail. If a nail is unaffected, it will be recorded as such and will not contribute to the total mNAPSI score.

If any of the 7 response items that contribute to mNAPSI is present, while other items are missing (ie, partial mNAPSI data), then the missing items are assumed to be 0 for the mNAPSI calculation. In some cases, the data may be captured in such a way that only non-zero component scores are present in the database. Again, those components that are not present are simply assumed to be 0 for the mNAPSI calculation.

Change from Baseline in mNAPSI score for subjects with nail PSO at Baseline is defined as Post-Baseline mNAPSI score minus Baseline mNAPSI.

An mNAPSI75 responder is defined as a subject who achieved at least a 75% improvement from Baseline in the mNAPSI score. mNAPSI90 and mNAPSI100 are defined accordingly. The proportion of mNAPSI75/90/100 responders for subjects with nail PSO at Baseline over time will be summarized for each study period (Initial randomized, Maintenance) by treatment group and OLE by treatment sequence.

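### The PASI missing-item rule has no exception for a region whose recorded area (or severities) already fixes its contribution at 0, so if such records occur it can inflate PASI or set a clear subject to missing

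*SAP*

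**What the plan says.** SAP Section 8.1.1.1 builds PASI from four regional products, (R+T+S) x A, weighted 0.1 (head), 0.2 (upper extremities), 0.3 (trunk) and 0.4 (lower extremities). The area grade runs from "0 for no involvement; up to 6 for 90% - 100% involvement", and for the total score "the lowest is 0 for no psoriasis lesions".

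The same section gives three rules for missing items:

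- "If a subject is missing 1 or 2 severity measurements for a certain region", the mean of the remaining severities in that region is used. This does not help a region with all three blank.
- The substitution rule begins: "If the area of affected skin and/or all severity measurements for up to 2 regions are missing, then the missing (R+T+S) x A". Its second half defines the replacement value, saying that the product "will be substituted by the average of the available (R+T+S) x A".
- Where more than two regions are affected, the fallback applies: "Otherwise, the PASI will be set to missing".

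Section 4.2.1 treats a variable that such a rule sets to missing as completely missing. For the primary endpoint, Section 8.1.2 then says that any subject "who has missing data for the primary efficacy variables at the Week 16 time point will be considered a nonresponder". Section 8.2.2 uses non-responder imputation for PASI100 at Week 48 as well.

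For another instrument, mNAPSI, Section 8.3.9 notes: "In some cases, the data may be captured in such a way that only non-zero component scores are present in the database". It sets absent components to 0. PASI has no comparable sentence.

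**The concern.** The trigger for substitution is a missing item, not a product that cannot be determined. These differ in two situations: area recorded as 0 with all severities blank, and severities all recorded as 0 with the area blank. In both, the SAP's own formula gives 0, yet the rule as written discards that and either borrows from other regions or contributes to setting PASI to missing.

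Two things are at stake. Partly clear subjects can receive an inflated PASI, which bears on PASI75, PASI90, the absolute PASI categories and percent change. Completely clear subjects can lose a recorded PASI100 and count as failures for H1 and H2 (Week 16) and H4 to H6 (Week 48). Section 4.2.1 justifies non-responder imputation on the ground that absent data suggest an ineffective treatment. Here the recorded data would show the reverse.

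The missing-data sensitivity analyses do not put the recorded 0 back. The observed-case analysis drops the subject, LOCF takes an earlier score, and multiple imputation draws a value.

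**Working it through.** **Inputs.** Formula, weights and missing-item rules from SAP Section 8.1.1.1. Rates of 60% and 44% and 350 subjects per arm from Section 2.4. Two-sided alpha of 0.05 from Section 4.5. Baseline PASI of at least 12 from Section 2.3.1. The Baseline of 22 and the item patterns are illustrations.

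**1. The plan's own power.** SE = sqrt(0.60 x 0.40/350 + 0.44 x 0.56/350) = 0.0373. Power = Phi(0.16/0.0373 - 1.96) = 99.0%. With a pooled null variance it is 98.9%, and with a continuity correction 98.7%. The stated 98% is reproduced within rounding and method.

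**2. Partly clear, two regions clear with severities blank.** Trunk and legs have R=T=S=1 and area score 1, so each product is 3. Head and upper extremities have area score 0 and blank severities.

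- From the formula: 0.3 x 3 + 0.4 x 3 = 2.1.
- Rule as written: the average of the available products is (3+3)/2 = 3, given to both clear regions. PASI = 2.1 + 0.1 x 3 + 0.2 x 3 = 3.0.
- From Baseline 22: (22 - 2.1)/22 = 90.5% against (22 - 3.0)/22 = 86.4%. PASI90 is lost.

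**3. Other partly clear patterns, Baseline 12.** Trunk and legs are clear with severities blank in each.

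| Other regions | PASI by formula | PASI as written | Improvement |
|---|---|---|---|
| Head and arms: area 1, severities 1/1/1 | 0.9 | 3.0 | 92.5% vs 75.0% |
| Head: area 1, 1/1/1; arms fully recorded as 0 | 0.3 | 1.35 | 97.5% vs 88.8% |
| Head and arms: area 2, severities 2/1/1 | 2.4 | 8.0 | 80.0% vs 33.3% |

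The first two rows lose PASI90, and the second also leaves the PASI <=1 category. The third loses PASI75. If only the head is involved (area 1, 1/1/1) and the other three regions are clear with severities blank, PASI is 0.3 by formula and missing as written.

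**4. Completely clear subject (area 0 in all four regions).**

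| Regions with severities blank | PASI as written | PASI100 |
|---|---|---|
| 1 or 2 | 0 (an average of zeros) | responder, correct |
| 3 or 4 | missing | non-responder by imputation, wrong |

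**5. What it could cost on the primary endpoint.** The documents give no frequency, so f below is an assumption: the share of truly clear subjects, equal in both arms, whose PASI becomes missing. Rates are 0.60(1 - f) and 0.44(1 - f). Power uses the formula in step 1.

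| f | Rates | Difference | Power |
|---|---|---|---|
| 0 | 60.0% / 44.0% | 16.0 points | 99.0% |
| 5% | 57.0% / 41.8% | 15.2 points | 98.3% |
| 10% | 54.0% / 39.6% | 14.4 points | 97.1% |
| 20% | 48.0% / 35.2% | 12.8 points | 93.4% |

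**The case against.** The strongest reply is that the triggering record may never exist. Section 8.1.1.1 gives a clear region its own severity score of 0, and nothing in the SAP says severities are skipped when the area is 0. If the CRF requires those zeros, the defect has no effect. This stands, and it limits the point to a conditional one.

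A reader might take the mNAPSI sentence as a sign that the same capture pattern was expected for PASI. The documents do not support that. For mNAPSI only affected nails are scored, so absent components are normal there, while PASI rates all four regions. The contrast shows a rule that could have been written, not that PASI blanks occur.

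It can also be said that what is replaced is a missing product, and a product with area 0 is not missing. That reading is possible, but the stated condition is a missing area or missing severities. Two programmers could therefore derive different values for the primary endpoint.

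Finally, equal losses in both arms shrink the difference and so do not favour bimekizumab on superiority. Even at f = 20%, the distance from the non-inferiority margin is (0.128 + 0.10)/0.0369, about 6 standard errors. This stands too.

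**Conclusion.** The rule misfires on its literal wording: it overrides a contribution that the SAP's own formula has already fixed at 0. The consequences are specific.

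- One or two such regions with at least one non-zero available region: PASI is too high. That subject is not a PASI100 responder in any case, so only PASI75, PASI90, absolute PASI and percent change are affected.
- Three or four such regions in a completely clear subject: PASI is missing and PASI100 is wrongly scored as non-response.

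A reader might infer that any blank in a clear region costs a PASI100 response. It does not, because with one or two such regions the rule averages zeros and returns 0. A reader might also infer that the trial's power or primary result is compromised. The documents do not support this: the 98% is not in error, the 5% to 20% range is illustrative, and the true frequency is unknown and may be zero. The point is worth correcting because it concerns the derivation of the primary endpoint and is cheap to settle.

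**What to change.** Insert before the substitution rule in Section 8.1.1.1:

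> If the area score of a region is 0, or its redness, thickness and scaliness are all recorded as 0, (R+T+S) x A for that region is 0, the region counts as available and is not substituted.

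Apply substitution and the set-to-missing rule only to the remaining regions, at Baseline and at every visit.

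The cost is one sentence and a small change in the derivation program, with one real downside. Week 48 results already exist, and the footnotes to Table 12-3 (Appendix D) have those analyses re-run at Week 144 and at the final analysis, so a re-run could differ from the interim report. Record the change as a dated clarification, and report the number of affected records by arm and visit together with any change in responder status. If the count is zero, a statement to that effect closes the point.

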### 8.1.2 Primary analysis of the primary efficacy variable

The analysis of the primary efficacy variable (PASI100 at Week 16) will be based on the RS. A stratified Cochran-Mantel-Haenszel (CMH) test will be performed, where region and prior biologic exposure (yes/no) will be used as stratification variables.

Treatment comparisons between bimekizumab and secukinumab will be made based on the CMH test using the p-value for the general association. For the assessment of non-inferiority, a non-inferiority margin of 10% will be used and evaluated based on the CI for the stratified Mantel-Haenszel risk difference between bimekizumab and secukinumab. The evaluation of superiority will use pairwise treatment comparisons based on the CMH test using the p-value for the general association. The odds ratio and associated confidence interval (CI) based on the Wald test will be presented.

To calculate the stratified Mantel-Haenszel risk difference, the method of Greenland and Robins (1985) is used. For each combination of strata, a 2x2 table of treatment group and response is created. A theoretical 2x2 table for a given stratum is shown below, where n = a+b+c+d.

Treatment Group	Response	
	Yes	No
Bimekizumab	a	c
Secukinumab	b	d

Given that structure, the stratified Mantel-Haenszel risk difference, standard error, and two-sided (1-α)\*100% confidence interval may be written as follows:

$$RD_{MH} = \frac{\sum_i ((a_i * (b_i + d_i) / n_i) - (b_i * (a_i + c_i) / n_i))}{\sum_i ((a_i + c_i) * (b_i + d_i) / n_i)}$$

$$SE_{MH} = \sqrt{\frac{\sum_i \left\{ \frac{[a_i * c_i * (b_i + d_i)^3] + [b_i * d_i * (a_i + c_i)^3]}{(a_i + c_i) * (b_i + d_i) * n_i^2} \right\}}{\left\{ \sum_i \left[ \frac{(a_i + c_i) * (b_i + d_i)}{n_i} \right] \right\}^2}}$$

$$CI_{MH} = RD_{MH} \pm \text{probit}(1 - (\alpha/2)) * SE_{MH}$$

For the assessment of non-inferiority of bimekizumab to secukinumab, the lower 97.5% confidence limit for the stratified Mantel-Haenszel risk difference will be considered. If that value is greater than -10%, then non-inferiority will have been established.

NRI will be used to account for missing data in the primary analysis. Specifically, any subject who withdraws from IMP prior to Week 16 or who has missing data for the primary efficacy variables at the Week 16 time point will be considered a nonresponder.

The number and percentage of subjects who are PASI100 responders at Week 16 will be summarized.

A line plot of the percentage improvement from Baseline in PASI score over time by treatment group will be produced by randomized treatment group for the RS and repeated for the MS. An additional plot will be produced for the OLS by OLE treatment groups.

By-subject listings of PASI and PASI responder variables will be provided for the Initial and the Maintenance periods combined based on RS. This listing will also be provided separately for the OLE and the OLE2 treatment periods.

### 8.1.3 Supportive and sensitivity analyses of the primary efficacy variable

The following sensitivity analyses for the primary efficacy variable will be performed to evaluate the assumptions related to the handling of missing data

#### 8.1.3.1 Sensitivity Analysis #1

Missing data will be addressed by using MI (MCMC) method for intermittent missing data, followed by monotone regression for monotone missing data (see Section 4.2.1.6) to evaluate the effect of the method for handling missing data on the analysis. The actual PASI scores will be imputed and then dichotomized to obtain the response status. The treatment differences for each imputed data set will subsequently be evaluated using the stratified CMH test as used in the primary analysis. The results from each of the imputed data sets will be combined for overall inference using Rubin's rules, which account for the uncertainty associated with the imputed values (Rubin, 1987). This will be done using SAS PROC MIANALYZE. This procedure assumes a MAR pattern of missingness and corresponds to an estimand of the difference in outcome improvement if all subjects tolerated or adhered to treatment (Mallinckrodt et al, 2012). This is an estimand of efficacy to evaluate the de jure hypothesis.

#### 8.1.3.2 Sensitivity Analysis #2

This sensitivity analysis will be based on observed data at Week 16. Subjects with missing data or who have prematurely discontinued IMP will be treated as missing (see Section 4.2.1.5). The same stratified CMH test as in the primary efficacy analysis will be used.

### **8.1.3.3 Sensitivity Analysis #3**

The primary efficacy analyses from Section 8.1.2 will be repeated using LOCF as the imputation method (see Section 4.2.1.5).

### **8.1.3.4 Sensitivity Analysis #4**

The primary efficacy analyses from Section 8.1.2 will be repeated based on the FAS and the PPS.

### **8.1.3.5 Sensitivity Analysis #5**

As a sensitivity analysis to the primary analysis method, logistic regression based on the RS will be used. The odds ratio of the responder rates at Week 16 will be estimated and tested between treatment groups using a logistic regression model with factors of treatment group, region, and prior biologic exposure (yes/no). The odds ratio, associated confidence interval (CI), and p-value based on the Wald test will be presented. If the logistic regression model is unable to converge, then prior biologic exposure may be dropped from the model to facilitate convergence. If the model is still unable to converge, then region may be removed from the model as well. In addition, if the logistic regression model cannot converge, then Fisher's exact test will be used for inferential comparisons. As with the primary analysis, missing data will be handled using NRI.

### **8.1.3.6 Sensitivity Analysis #6**

The center-by-treatment interaction will be tested by replacing region with center in the logistic regression model described in Section 8.1.3.5 and adding a center-by-treatment interaction term. In the model, center will be based on the original centers prior to pooling. However, if the model is unable to converge due to a low number of subjects at a given center, a pooling (see Section 3.7) will be described in order to allow the model to converge. In order to obtain reasonable estimates of variability for a treatment arm at a given center, a minimum of 10 subjects will be considered acceptable for a center to be included in the model without pooling. Given the 1:1 randomization allocation scheme at the start of the study, this should provide a minimum of about 5 subjects in each treatment group. Centers with fewer than 10 subjects will be eligible for pooling. The pooling algorithm used is described in Section 3.7. In order to achieve model convergence, region may be used instead of center or prior biologic exposure may be dropped from the model. If convergence still cannot be achieved, this analysis will not be performed.

If the center-by-treatment interaction is not found to be significant ( $\alpha=0.10$ ), then no further analyses will be performed. On the other hand, if the interaction is significant, further analyses will be conducted to determine which center or centers may be the source of interaction. This will be done by running the logistic regression model (including the interaction term) where each center will be systematically removed from the model. This impact of a given center will be based on the change in the interaction p-value when that center is removed. The center or centers that appear to be driving the significant interaction effect will then be removed from the model to verify that conclusions remain the same with or without the influential center(s). This sensitivity analysis will be based on RS with NRI for missing data.

